10. ANALYSIS OF PHARMACOKINETICS

10.1. MEASUREMENTS

The Dose Selection Safety Population will be used for all individual plasma concentration listings, whilst all listings and summaries and pharmacokinetic analyses of PK data will be performed using the Dose Selection PK Population.

PK endpoints include plasma concentrations of nalbuphine and its corresponding metabolites (M1, M3, M4, and M5) at each collection time point and the derived PK parameters listed in Section 4.2.3.

10.2. PK SAMPLING SCHEDULE

During the Dose Selection Phase, blood samples will be collected at the following time points:

- Pre-dose and at 0.25, 0.5, 1, 1.5, 2, 2.5, 3, 4, 5, 6, 8, 10, 12 and 24 hours post-dose.

10.3. DERIVED AND IMPUTED DATA

- PK parameters (C_{max} , t_{max} , AUC_{last} , AUC_{inf} , $t_{1/2}$, k_{el} , CL/F and Vd/F) will be determined for nalbuphine and its metabolites based on concentrations in plasma and actual sampling times via non-compartmental analysis using validated Phoenix WinNonlin Version 6.4 or higher. For each subject, the PK parameters will be derived as follows: The apparent C_{max} and the corresponding t_{max} will be read directly from the concentration-time plot (observed data, not predicted data by the program);
- AUC_{last} and AUC_{inf} will be calculated using the linear up log down trapezoidal method;
- The elimination rate constant (k_{el}) will be determined by log-linear regression obtained on at least the three last quantifiable concentrations;
- The Terminal elimination half-life ($t_{1/2}$) will be calculated as $0.693/k_{el}$.
- AUC_{inf} is calculated by the program as:
 $AUC_{inf} = AUC_{last} + AUC_{t-inf}$ where t is the sampling time point of the last measurable concentration (t_{last}). AUC_{t-inf} is calculated by the program as: C_{last}/k_{el} , where C_{last} is the last measurable concentration at time t and k_{el} is the elimination rate constant during the terminal elimination phase;
- CL/F will be derived by $Dose/AUC_{inf}$ and Vd/F will be derived as CL/F divided by k_{el} .

The following reliability criteria will be used for the PK parameters:

- The adjusted square of the correlation coefficient (Rsquare adj.) for the goodness of fit of the regression line through the data points must be at least 0.80 for the k_{el} value to be considered reliable;
- The AUC extrapolation to infinity (AUC_{t-inf}) must be $\leq 20\%$ of the total area for AUC_{inf} to be considered reliable;

For subjects with unreliable k_{el} (e.g. Rsquare adjusted ≤ 0.80), k_{el} , $t_{1/2}$ and AUC_{inf} will be flagged in the individual data Listings. For subjects with unreliable AUC_{inf} (because of extrapolation $>20\%$), AUC_{inf} , CL/F and Vd/F will be flagged in the individual data Listings. Flagged PK parameters will be excluded from summarization and statistical analyses.

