3.6. ADMINISTRATION OF STUDY MEDICATION

Subjects will be administered study drug with a flavored, low caloric, artificially sweetened, non-carbonated beverage (e.g., diet cranberry cocktail). Each subject will receive a single oral dose of either nalbuphine HCl solution or matching placebo after at least an 8-hour fast. The actual doses administered in each cohort may be adjusted (increased, decreased or repeated) based on the evaluation of safety data obtained in previous cohorts. Additional cohorts of subjects may be added to those planned in Table 1 until the MSD is identified. Higher doses can be up to 50% greater than the dose administered in the previous cohort, based on supporting safety data. The dosing solution (150 mL) will be administered in a dark bottle. After subjects drink the dosing solution, an additional 50 mL of flavored beverage will be added to the dosing container as a rinse and then administered to the subjects. The start of dosing will be considered time zero and subjects will be informed that the duration allocated for dosing will be 5 minutes.

There are 7 planned cohorts (Table 1). All subjects within a cohort will receive the same dose of nalbuphine HCl solution if randomized to the active drug. Dose escalation procedures are described in Section 4.9 of the Protocol.

Table 1 Planned Oral Doses of Nalbuphine Hydrochloride Solution in the Dose Selection Phase

Cohort (n=8)	Nalbuphine Free Base Dose Level	Nalbuphine HCl Equivalent Dose	Nalbuphine HCl Solution (n=6)	Placebo Solution (n=2)
1	81 mg	90 mg	9 mL × 10 mg/mL + 141 mL flavored beverage	150 mL flavored beverage
2	108 mg	120 mg	12 mL × 10 mg/mL + 138 mL flavored beverage	150 mL flavored beverage
3	135 mg	150 mg	15 mL × 10 mg/mL + 135 mL flavored beverage	150 mL flavored beverage
4	162 mg	180 mg	18 mL × 10 mg/mL + 132 mL flavored beverage	150 mL flavored beverage
5	243 mg	270 mg	27 mL × 10 mg/mL + 123 mL flavored beverage	150 mL flavored beverage
6 ^a	Up to 365 mg	405 mg	40.5 mL × 10 mg/mL + 109.5 mL flavored beverage	150 mL flavored beverage
7 ^a	Up to 486 mg	540 mg	54 mL × 10 mg/mL + 96 mL flavored beverage	150 mL flavored beverage

HCl=hydrochloride.

^a The dose of nalbuphine free base in Cohorts 6 and 7 may increase up to a 50% increase from the preceding dose but not to exceed 486 mg (3 fold the therapeutic dose) based on the evaluation of safety data in the previous cohorts.

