4. ENDPOINTS

4.1.1. Pharmacokinetic Endpoints

The PK parameters that will be evaluated for nalbuphine, as applicable, include:

- C_{max} : maximum observed plasma concentration
- t_{max} : time to maximum observed plasma concentration
- AUC_{last} : area under the plasma concentration versus time curve from time 0 to the last measurable concentration

The following parameters will be derived for nalbuphine if sufficient data are available:

- AUC_{inf} : area under the plasma concentration versus time curve extrapolated to infinity
- k_{el} : first-order elimination rate constant associated with the terminal (log-linear) portion of the curve
- $t_{1/2}$: apparent first-order terminal elimination half-life will be calculated as $0.693/k_{el}$
- CL/F : apparent clearance
- Vd/F : apparent volume of distribution

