10.5. DATA SUMMARIZATION AND PRESENTATION

PK sample collection data, plasma concentrations and the derived PK parameters for nalbuphine and its metabolites (M1, M3, M4, and M5) will be listed by subject. Plasma concentration data and the PK parameters for the nalbuphine treatments and its metabolites will be summarized by dose level using the following statistics (Table 5):

Table 5 Summary Statistics for PK Analyses

Variable	Summarized with:
Plasma concentration at each time point	n; number of missing (if not zero); number and percent BLQ values; arithmetic mean, SD and coefficient of variation (CV%, calculated as 100*SD/mean); minimum, median and maximum
C _{max} , AUC _{last} , AUC _{inf} , CL/F, Vd/F	n; number of missing (if not zero); arithmetic mean, SD and coefficient of variation (CV%, calculated as 100*SD/mean); minimum, median, and maximum; geometric mean and geometric CV% (calculated as $100\% \times \sqrt{e^{z^2} - 1}$, where z^2 is the variance of the log-transformed data)
t _{max}	n; number of missing (if not zero); median, minimum, maximum, first quartile (Q1) and third quartile (Q3).
t _{1/2} , k _{el}	n; number of missing (if not zero); arithmetic mean, SD and CV (%); minimum, median, and maximum

AUC = area under the curve; BLQ = below the limit of quantification; C_{max} = maximum observed plasma concentration; CV = coefficient of variation; SD = standard deviation; t_{max} = time to maximum plasma concentration; t_{1/2} = terminal elimination half-life; k_{el} = first-order elimination rate constant.

If more than 50% of values are BLQ or are missing, then only n, n (%) BLQ, minimum, median and maximum will be calculated and reported. If the calculated mean/median value is less than LLOQ, then that time point will be ignored for plotting the mean PK profiles.

The following graphical presentations will be made for nalbuphine:

- Mean PK plasma concentrations plotted vs time curve by dose level within the same figure using both linear and log-linear scales.
- Box-whisker plots of PK parameters including C_{max} and AUC_{last} by dose level using linear scale.
- By-subject time-concentration curves by dose level within the same figure using both linear and log-linear scales.

The PK parameters summary will be presented separately for a subset (if applicable) of subjects who do not vomit within 12 hours of dosing.

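### SAP 10.3 applies the CL/F and Vd/F formulas to the four metabolites, which are not dosed, so those outputs would be labelled clearance and volume without being comparable to CL/F and Vd/F

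*SAP*

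**What the plan says.** SAP 10.1 sets the analytes: "PK endpoints include plasma concentrations of nalbuphine and its corresponding metabolites (M1, M3, M4, and M5) at each collection time point", together with derived parameters. For the parameter list it points to a Section 4.2.3, but Section 4 of the SAP contains only 4.1.1 to 4.1.3.

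SAP 10.3 names Cmax, tmax, AUClast, AUCinf, t1/2, kel, CL/F and Vd/F and says they "will be determined for nalbuphine and its metabolites based on concentrations in plasma and actual sampling times via non-compartmental analysis". The formulas follow: "CL/F will be derived by" dose over AUCinf, and "Vd/F will be derived as CL/F divided by" kel. Neither formula is restricted to nalbuphine. The reliability rules in the same section concern only the regression fit and the extrapolated share of AUC.

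SAP 10.5 carries this into reporting: "Plasma concentration data and the PK parameters for the nalbuphine treatments and its metabolites will be summarized by dose level", using Table 5, which has a row containing CL/F and Vd/F. The indexes of tables and listings include Table 14.2.2.2 and Listing 16.2.6.2.2, both covering PK parameters of nalbuphine and the four metabolites.

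The endpoint sections are worded for the parent. SAP 4.1.1 introduces AUCinf, kel, t1/2, CL/F and Vd/F with "The following parameters will be derived for nalbuphine if sufficient data are available". SAP 4.1.3 and protocol 2.2.4 place the same parameters within a nalbuphine endpoint. Protocol 8.1.4 asks for metabolite parameters in Part A without saying which.

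**The concern.** CL/F can be read as an apparent clearance because the dose in the numerator is the dose of the substance whose AUC is in the denominator. SAP 3.6 has each subject take nalbuphine HCl solution or placebo; no metabolite is given. For M1, M3, M4 and M5 the numerator would be the parent dose, and the result would depend on how much of the parent becomes that metabolite. Vd/F is built on the same number and inherits the problem.

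A programmer following SAP 10.3 and 10.5 would produce these values. In an escalation study that watches for departures from linear exposure, a dose trend in a metabolite value labelled clearance could be read as a change in elimination when it reflects absorption or formation.

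**Working it through.** The plan states no figure to reproduce here, so the check is a mass-balance identity, an illustration and a count.

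**Parent.** AUC = F × Dose/CL, so Dose/AUCinf = CL/F. Protocol 1.1 gives mean AUC0-inf of 58.8 ng·h/mL at 27 mg and 328 ng·h/mL at 162 mg. These come from earlier healthy-subject single-dose data, not the Part A solution cohorts.
- 27,000,000 ng / 58.8 ng·h/mL = 459 L/h
- 162,000,000 ng / 328 ng·h/mL = 494 L/h

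Both are usable apparent clearances.

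**Metabolite.** Apart from the molecular-weight ratio, AUCm = F × fm × Dose/CLm, so Dose/AUCm = CLm/(F × fm). This exceeds CLm/F by the factor 1/fm. Equivalently, it is nalbuphine CL/F multiplied by parent AUC over metabolite AUC, so it adds nothing to the AUC ratio except a label.

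**Illustration.** F = 0.16 is from protocol 3.2.1. Everything else is assumed: CL 80 L/h, V 900 L, CLm 30 L/h, Vm 60 L, ka 2/h, and fm from 0.05 to 0.90. The reference values are CLm/F = 30/0.16 = 187.5 L/h and Vm/F = 60/0.16 = 375 L. A one-compartment parent–metabolite model, integrated numerically, returned 500 L/h for the parent, equal to 80/0.16. For the metabolite it gave:

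| fm (assumed) | Dose/AUCm (L/h) | ratio to CLm/F | Vd/F by the SAP formula (L) |
|---|---|---|---|
| 0.05 | 3,750 | 20 | 42,188 |
| 0.10 | 1,875 | 10 | 21,094 |
| 0.25 | 750 | 4 | 8,438 |
| 0.50 | 375 | 2 | 4,219 |
| 0.90 | 208 | 1.1 | 2,344 |

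The volume is distorted a second time. In this example the metabolite's terminal slope is the parent's (80/900 = 0.089/h) rather than its own (30/60 = 0.5/h), because formation limits its decline.

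The model leaves out first-pass formation and the molecular-weight ratio. With first-pass formation, F × fm is replaced by the fraction of the oral dose reaching the circulation as that metabolite, which the documents also do not give. The table shows how strongly the value depends on an unstated fraction; it does not predict the size or direction in this trial.

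**Count.** 4 metabolites × 2 parameters = 8 per dose level. Across 5 planned dose levels (SAP 3.2) or 7 (SAP 3.6, Table 1), that is at most 40 or 56 summaries. Values are lost where extrapolation exceeds 20% or a profile is entirely BLQ.

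**The case against.** The strongest reply is that little turns on these numbers. No hypothesis test uses CL/F. The planned figures show concentrations, Cmax and AUClast. Protocol 1.1 reports the metabolites to be pharmacologically inactive. The plateau review in protocol 4.9.2 concerns nalbuphine exposure, and SAP 2.1 and 5 say Part A was already complete. All of that stands. A reader might infer that dose escalation or the maximum safe dose was at risk; the documents do not support this.

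A second reply is that the values are not meaningless. CLm/(F × fm) is an apparent quantity, and parent CL/F is itself scaled by F. That is fair: the fault is a misleading label and lack of comparability. The fraction formed is also only absent from these documents, not shown to be unknown.

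Third, a reader might infer that SAP 4.1.1 singles out CL/F and Vd/F as parent-only and that 10.3 flatly contradicts it. It does not single them out: 4.1.1 names all eight parameters for nalbuphine, and read strictly it would also remove the metabolite Cmax and AUC, which fall within what protocol 8.1.4 asks for. Nor does protocol 2.2.3.2 help, since it lists Main Study (Part B) endpoints; the Part A text is 2.2.4. The point rests on the pharmacokinetics, with which the endpoint sections are merely consistent.

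Fourth, the table shells are an attachment not included in the documents and may already omit these rows. The SAP text does not.

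Finally, SAP 3.6 Table 1 has a free-base column and a "Nalbuphine HCl Equivalent Dose" column, and 10.3 does not say which one Dose means. A reader might call that a second error. The dose levels are headed and discussed as free base, so that is the natural reading. Using salt would shift nalbuphine CL/F and Vd/F by a constant 180/162 = 1.111, or 11.1%, which cannot create a dose trend.

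**Conclusion.** The point holds for the four metabolites. As written, SAP 10.3 and 10.5 direct the reporting of parent dose over metabolite AUC as CL/F, and a volume derived from it, for M1, M3, M4 and M5. Nothing in either document exempts the metabolites, defines a metabolite dose or supplies a fraction formed.

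Eight values per dose level is an upper bound, not a certainty for every cohort. The 1.1- to 20-fold range rests on assumed fractions and a simplified model. The effect is limited to exploratory, descriptive PK output; nalbuphine PK, the safety analysis and the maximum safe dose decision are untouched. The free-base question is a clarification only.

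**What to change.** In SAP 10.3, 10.5 and Table 5, and in Table 14.2.2.2 and Listing 16.2.6.2.2, limit CL/F and Vd/F to nalbuphine. Keep Cmax, tmax, AUClast, AUCinf, kel and t1/2 for the metabolites, which meets protocol 8.1.4. If an index of metabolite formation is wanted, add metabolite-to-parent AUC ratios under that name. While editing 10.3, state that Dose is the free-base dose, and check that the table and listing shells agree.

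The cost is a few lines of SAP text and the removal of up to two parameters per metabolite from one table and one listing. No data collection or assay work changes.

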#### 8.1.4 Analysis of Pharmacokinetics

Pharmacokinetic analyses will be performed using the Dose Selection PK population in Part A and the PK population in Part B.

The PK parameters for plasma nalbuphine and (Part A only) its metabolites will be calculated using non-compartmental analysis and will be summarized by dose level in Part A and by treatment in Part B. Graphs of the concentration (original and log transformed) versus time will be generated. Descriptive statistics, including n, mean, SD, coefficient of variation (CV), minimum, median, and maximum will be calculated by dose level (Part A) and treatment (Part B) and time point for each study drug. Concentrations below the limit of quantification (BLQ) will be set to zero for the generation of summary statistics for concentrations and the generation of mean concentration-time plots.

For the calculation of the PK parameters, concentration-time data will be treated as follows: BLQ concentrations before the first quantifiable concentration will be set to zero; BLQ concentrations after the first quantifiable concentration will be treated as missing; and pre-dose sampling times relative to dosing will be set to zero. Descriptive statistics, including n, mean, SD, geometric mean, geometric CV, minimum, median, and maximum, will be calculated by dose level and treatment group for all PK parameters except  $T_{max}$ ,  $t_{1/2}$ , and kel. Time to maximum observed plasma concentration data will be summarized with minimum, median, maximum, Q1 and Q3. The  $t_{1/2}$  and kel data will be summarized with n, mean, SD, CV, minimum, median, and maximum.

PK profiles will be analyzed for all subjects, even if some PK sampling time points are missed. The PK parameters will be subject to quality control criteria. If quality control criteria are met, the PK parameters will be used in analyses and models. Quality control criteria for PK will be sufficient to eliminate unreliable data. Details will be provided in the SAP.

The PK parameters summary will be presented separately for a subset (if applicable) of subjects who do not vomit within 12 hours of dosing in Part A and Part B of the study.

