AUC _{inf}	Concentrations C _i at times t _i ; C _{last} and k _{el}	$AUC_{inf} = AUC_{last} + AUC_{t-inf}$ 
where t is the sampling time point of the last measurable concentration. AUC_{t-inf} is calculated as: C_{last}/k_{el}, where C_{last} is the last measurable concentration taken directly from the raw data.
	
The AUC_{t-inf} must be ≤ 20% of the total area for AUC_{inf} to be considered reliable. For subjects with unreliable AUC_{inf} (because of extrapolation >20%), AUC_{inf} will be flagged in the individual data.

k _{el}	Concentrations C _i at times t _i	
First order elimination rate constant (k_{el}) associated with the terminal (log-linear) portion of the curve (the negative gradient
	
At least three samples are needed during the terminal log-linear phase in order to reliably estimate the terminal rate constant. The adjusted

Derived Variable	Variables used	Calculation	Notes
		of the regression of log-concentration versus time in the elimination phase).	square of the correlation coefficient (R-square adjusted) for the goodness of fit of the regression line through the data points must be at least 0.85 for the k_{el} value to be considered reliable. k_{el} , $t_{1/2}$ and AUC_{inf} will be flagged in the individual data Listings if k_{el} value is not reliable.
$t_{1/2}$	Concentrations C_i at times t_i	Half-life ($t_{1/2}$), the time for half the drug to be eliminated is calculated as $\ln(2)/k_{el}$	Terminal elimination half-life, calculated as $\ln(2)/k_{el}$. If the time interval between the lower and upper time points used for the regression spans is less than the derived half-life itself then k_{el} and the associated $t_{1/2}$ will be considered unreliable. k_{el} , $t_{1/2}$ and AUC_{inf} will be flagged in the individual data listings if k_{el} and the associated $t_{1/2}$ value are not reliable. Flagged PK parameters will be excluded from summarization and statistical analyses.
Derived PD parameters:			
E_{max}	Response at time i (E_i) over one inter-dosing interval	$\text{Max}_i \{E_i\}$	Missing data are ignored
E_{min}	Response at time i (E_i) over one inter-dosing interval	$\text{Min}_i \{E_i\}$	Missing data are ignored

Derived Variable	Variables used	Calculation	Notes
TE _{max}	Response at time i (E _i) at times t _i over one inter-dosing interval Time at time i (time_i)	$TE_{\max} = \max_j \{t_j \mid E_j > E_i \forall i\}$	The first time of peak response is used if the peak is obtained more than once

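### The SAP sets two adjusted R-squared cut-offs for a reliable kel (0.80 and 0.85), and leaves CL/F and Vd/F in the summaries when the kel behind them is rejected

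*SAP*

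**What the plan says.** SAP 10.3 estimates kel from a regression that "will be determined by log-linear regression obtained on at least the three last quantifiable concentrations"; the number of points has a minimum but no other rule. It then lists reliability criteria. The adjusted R-squared of the "regression line through the data points must be at least 0.80 for the" kel value to be accepted, and the extrapolated area must be no more than 20% of AUCinf.

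Two flagging sentences follow. For an unreliable kel, illustrated by "e.g. Rsquare adjusted ≤ 0.80", the parameters flagged are kel, half-life and AUCinf. For an AUCinf that is unreliable because extrapolation exceeds 20%, AUCinf is flagged and "CL/F and Vd/F will be flagged in the individual data Listings. Flagged PK parameters will be excluded from summarization and statistical analyses".

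Appendix A, in the kel row, sets a different bar: the "regression line through the data points must be at least 0.85 for the" kel value. Its half-life row adds a span rule: "If the time interval between the lower and upper time points used for the regression spans is less than the derived half-life itself", kel and half-life are unreliable. Both rows flag kel, half-life and AUCinf. Appendix A has no row for CL/F or Vd/F.

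Protocol 8.1.4 delegates the detail: "Quality control criteria for PK will be sufficient to eliminate unreliable data. Details will be provided in the SAP".

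**The concern.** The flags decide which subjects contribute to a summary, and each dose level has only about six active subjects. A profile with adjusted R-squared between 0.80 and 0.85 is kept under 10.3 and dropped under Appendix A, so n and the mean for kel, half-life and AUCinf depend on which page the programmer follows. Section 10.3 also disagrees with itself at exactly 0.80, which is both acceptable and an example of unacceptable.

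The second problem is one of logic. AUCinf contains Clast/kel, CL/F is Dose/AUCinf, and 10.3 states "and Vd/F will be derived as CL/F divided by" kel. If kel is not trusted, neither is anything built on it, yet CL/F and Vd/F pass through. A reader of Table 5 could then see more subjects in the CL/F and Vd/F rows than in the AUCinf and kel rows they derive from. The protocol's commitment to eliminate unreliable PK data is not met for these two parameters.

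**Working it through.** **Text comparison**

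| Rule | SAP 10.3 | SAP Appendix A |
|---|---|---|
| Adjusted R-squared for a reliable kel | ≥ 0.80 (but ≤ 0.80 given as unreliable) | ≥ 0.85 |
| Regression span shorter than half-life | not listed | kel and half-life unreliable |
| Flagged if kel is unreliable | kel, half-life, AUCinf | kel, half-life, AUCinf |
| Flagged if extrapolation > 20% | AUCinf, CL/F, Vd/F | AUCinf |

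The cut-offs are conventions, so there is no plan figure to reproduce.

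**Does the 20% rule catch bad fits anyway?** For a mono-exponential decline, the share of AUC beyond 24 h is 2^(−24/half-life). The half-life range in Protocol 1.1 is 6.6 to 9.6 h.

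- 6.6 h: 2^(−3.64) = 8.0%
- 9.6 h: 2^(−2.5) = 17.7%

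Both are below 20%, so a poor fit can pass the extrapolation rule.

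**Worked profiles.** Take half-life 6.6 h (true kel 0.1050), regression points 10, 12 and 24 h, and AUClast taken as exact. With three points, adjusted R-squared = 1 − 2(1 − R-squared).

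- *12 h value 1.7 times too high.* R-squared 0.912, adjusted 0.824. Section 10.3 keeps it; Appendix A rejects it.
- *12 h value 1.8 times too high.* R-squared 0.897, adjusted 0.794. Both sections reject kel (estimate 0.1221). Per unit of starting concentration, AUClast = (1 − 0.0804)/0.1050 = 8.756 and the extrapolated area = 0.0804/0.1221 = 0.659, a share of 0.659/9.415 = 7.0%. CL/F and Vd/F are therefore not flagged. Relative to truth, CL/F is 1.01 and Vd/F is 1.011 × 0.1050/0.1221 = 0.87.

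**How often?** The documents give no residual error and no upper limit on the regression window, so this is illustration only. Assumptions: 400,000 mono-exponential profiles per setting, lognormal error, AUClast exact, half-life 6.6 h and 9.6 h. The windows are the last three points (10, 12, 24 h), the best adjusted R-squared among the last 3 to 7 points, and all seven points from 4 to 24 h.

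Let p be the per-profile chance that kel is positive, adjusted R-squared is below 0.80 and extrapolation is at most 20%. The chance of at least one in a cohort of six is 1 − (1 − p)^6. Example, last three points, 20% error: p = 7.16% (6.6 h) and 9.15% (9.6 h), giving 1 − 0.9284^6 = 36.0% and 1 − 0.9085^6 = 43.8%.

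| At least one of six | 10% error | 20% error | 30% error |
|---|---|---|---|
| Rejected kel, CL/F and Vd/F kept: last 3 points | 0.2–4% | 36–44% | 67–74% |
| same: best fit, 3–7 points | about 0% | 3–15% | 38–52% |
| same: all 7 points | about 0% | 10–43% | 80–88% |
| Between 0.80 and 0.85: last 3 points | 1–11% | 25–34% | 33–35% |
| same: best fit, 3–7 points | 0–0.3% | 8–34% | 35–43% |
| same: all 7 points | 0–1% | 26–67% | 58–67% |

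A separate one-compartment simulation (absorption rate 4/h assumed, last three points, 20% error) gave p of 7.2% and 9.0%, in agreement.

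**How much does one retained subject move a six-subject mean?** (Last three points, 20% error; shift = |ratio to truth − 1|/6.)

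- Vd/F, half-life 6.6 h: median ratio 1.11 (5th–95th percentile 0.88–1.44). Typical shift 0.11/6 = 1.8%; upper tail 0.44/6 = 7.3%.
- Vd/F, half-life 9.6 h: median 0.96 (0.79–1.13). Typical shift 0.04/6 = 0.7%; tail 0.21/6 = 3.5%.
- CL/F: 5th–95th percentile 0.91–1.02 (6.6 h) and 0.98–1.08 (9.6 h). Largest of these shifts 0.09/6 = 1.5%.

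For scale, if Vd/F varied as much as the 46% quoted for AUC in Protocol 12.2 (an assumption), the standard error of a six-subject mean would be 46/√6 = 18.8%.

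**The case against.** The strongest reply is about weight. These are descriptive, exploratory Part A rows with no test on them. The planned box plots are of Cmax and AUClast, which do not use kel. PK review during escalation was optional, and Part A was complete when this SAP was updated. All of that stands and is why the point is minor.

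The frequencies rest on assumed error and window and run from about 0% to 88%, so they establish no rate. The half-life range used is of study means; Protocol 1.1 also gives 7 to 11 h in females, and at 11 h the expected extrapolated share is 22%, so the 20% rule catches more. The last-three-point figure at 20% error then falls to 31%. Possible enterohepatic circulation is not modelled. These limits stand too.

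The CL/F effect is very small because the extrapolated part is capped at 20%; the exposure is mainly in Vd/F. The boundary clash matters only at exactly 0.80.

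The span rule is operative in Appendix A, and the illustrative wording in 10.3 leaves room for it, so its absence there is an omission and not a conflict. Under the same assumptions, the chance of at least one profile in six passing 0.80, failing the span rule and extrapolating 20% or less was at most 0.2%; the rule therefore touches almost only the kel and half-life rows.

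One might also argue that an AUCinf rejected for a bad kel is already an unreliable AUCinf and takes CL/F and Vd/F with it. The text does not support that: the sentence that flags them is limited to extrapolation above 20%.

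**Conclusion.** The concern holds and is minor. The SAP gives contradictory cut-offs for the same parameter with no order of precedence, and its exclusion rule, followed literally, summarises CL/F and Vd/F from fits it has declared unreliable. Neither conclusion depends on a simulation.

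The likely numerical effect is a changed n and a small shift in a few descriptive rows: typically about 2% or less on a six-subject mean Vd/F from one retained subject, about 7% in the upper tail, and 1.5% or less on CL/F. Those sizes assume 20% residual error, a three-point regression and exact AUClast. No hypothesis test is affected.

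**What to change.** State one adjusted R-squared threshold, with one boundary convention, in both 10.3 and Appendix A. Add to 10.3 that when kel or AUCinf is unreliable for any reason, CL/F and Vd/F are also flagged and excluded. For tidiness, repeat the span rule in the 10.3 list so that all criteria stand together; this is optional.

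The cost is SAP wording and one flag in the PK program, with no new data. Slightly fewer CL/F and Vd/F values will be summarised per dose level. If outputs already exist, Protocol 8.1.2 provides for SAP changes to be outlined in the clinical study report, and the threshold actually applied should be stated there.
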